APPENDIX A: ECOG Performance Status Scale

Grade	Description
0	Normal activity. Fully active, able to carry on all pre-disease performance without restriction.
1	Symptoms, but ambulatory. Restricted in physically strenuous activity, but ambulatory and able to carry out work of a light or sedentary nature (e.g., light housework, office work).
2	In bed <50% of the time. Ambulatory and capable of all self-care, but unable to carry out any work activities. Up and about more than 50% of waking hours.
3	In bed >50% of the time. Capable of only limited self-care, confined to bed or chair more than 50% of waking hours.
4	100% bedridden. Completely disabled. Cannot carry on any self-care. Totally confined to bed or chair.
5	Dead.

APPENDIX B: New York Heart Association (NYHA) Functional Classification

NYHA Class	Symptoms
I	No symptoms and no limitation in ordinary physical activity, e.g., shortness of breath when walking, climbing stairs, etc.
II	Mild symptoms (mild shortness of breath and/or angina) and slight limitation during ordinary activity.
III	Marked limitation in activity due to symptoms, even during less-than-ordinary activity, e.g., walking short distances (20-100 m). Comfortable only at rest.
IV	Severe limitations. Experiences symptoms even while at rest. Mostly bedbound patients.

The Criteria Committee of the NYHA, Nomenclature and Criteria for Diagnosis of Diseases of the Heart and Great Vessels. 9th ed. Boston, Mass: Little, Brown & Co; 1994:253-256.

APPENDIX C: Medication Diary

Today's Date: _____

Agent: Pazopanib

Cycle: _____

Patient Name: _____

Study ID#: _____

1. Complete one form for each month. Take 800 mg of pazopanib once daily under fasting conditions (at least one hour before a meal or two hours after a meal). Take pazopanib with a glass of water and drink the glass of water in as little time as possible.
2. Record the date, the amount taken, and when you took it.
3. If you forgot to take your dose, you may make it up if there are more than 12 hours remaining before your next scheduled dose. Otherwise, restart pazopanib at the next scheduled dose.
4. If you have any questions or notice any side effects, please record them in the comments section. Record the time if you should vomit.
5. Please return the forms to your physician or your study coordinator when you go to your next appointment.

Day	Date	# of tablets taken	Dose time	Comments
1				
2				
3				
4				
5				
6				
7				
8				
9				
10				
11				
12				
13				
14				
15				
16				
17				
18				
19				
20				
21				
22				
23				
24				
25				
26				
27				
28				

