6.0 DOSE DELAYS/DOSE MODIFICATIONS

As a general rule, if dose reduction of pazopanib is necessary, the dose should be reduced stepwise by 200 mg at each step, and the subject should be monitored for approximately 10 to 14 days at each dose level. If toxicity does not abate during this monitoring time, the pazopanib may need to be interrupted and/or the dose further decreased with continued monitoring for an additional 10-14 days at each dose level, and so on.

If the toxicity has abated with reduction of the dose and dose re-escalation is considered safe by the investigator, the pazopanib dose can then be increased step-wise back to the pre-event dose

(in 200 mg increments, after monitoring for 10-14 days at each dose level to ensure that toxicity did not recur or worsen).

Dose-level	0	-1	-2	-3	-4
Dose	800 mg QD	600 mg QD	400 mg QD	200 mg QD	Discontinue

For patients at dose-level -3, 200 mg QD, a maximum dose delay of 14 days is allowed for management of toxicities. If toxicity does not resolve in 14 days, the patient should be discontinued from study.

Dose Modification Algorithms for Potential Treatment-Related Adverse Events

AE Terms & Descriptions	Dose Modification Algorithms
Hypertension	
(A). Asymptomatic and persistent SBP of ≥ 140 - <170 mmHg, or DBP ≥ 90 - <110 mmHg, or a clinically significant increase in DBP of 20 mmHg (but still below 110 mmHg).	Step 1. Continue pazopanib at the current dose. Step 2. Adjust current or initiate new antihypertensive medication(s). Step 3. Titrate antihypertensive medication(s) during next 2 weeks as indicated to achieve well-controlled ^a blood pressure (BP). If BP is not well-controlled within 2 weeks, consider referral to a specialist and go to scenario (B).
(B). Asymptomatic SBP ≥ 170 mmHg, or DBP ≥ 110 mmHg, or failure to achieve well-controlled BP within 2 weeks in scenario (A).	Step 1. Consider reducing or interrupting pazopanib, as clinically indicated. Step 2. Adjust current or initiate new antihypertensive medication. Step 3. Titrate antihypertensive medication(s) during next 2 weeks as indicated to achieve well-controlled BP. Step 4. Once BP is well-controlled, restart pazopanib dose-reduced by 200 mg if it was interrupted.

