(C). Symptomatic hypertension or recurring SBP ≥ 170 mmHg, or DBP ≥ 110 mmHg, despite modification of antihypertensive medication(s)	Step 1. Interrupt pazopanib. Step 2. Adjust current or initiate new antihypertensive medication(s). Step 3. Titrate antihypertensive medication(s) during next 2 weeks as indicated to achieve well-controlled BP. Referral to a specialist for further evaluation and follow-up is also recommended. Step 4. Once BP is well-controlled, restart pazopanib dose-reduced by 200 mg.
(D). Refractory hypertension unresponsive to above interventions.	Discontinue pazopanib and continue follow-up per protocol.
Proteinuria	
UPC <3	Continue pazopanib at the current dose; monitor as clinically indicated
UPC ≥ 3 or 24-h urine protein ≥ 3 g	Step 1. Interrupt pazopanib. Step 2. Weekly UPC or 24-hr urine protein monitoring until UPC is <3 or 24-hr urine protein is <3 g. Then restart pazopanib dose-reduced by 200 mg. Step 3. If UPC ≥ 3 or 24-h urine protein ≥ 3 g recurs, repeat steps 1 and 2 Step 4. If UPC ≥ 3 or 24-hr urine protein ≥ 3 g recurs and the pazopanib dose can no longer be reduced, discontinue pazopanib and continue follow-up per protocol.

AE Terms & Descriptions	Dose Modification Algorithms
Hemorrhage/Bleeding: Investigate and document underlying etiology of the bleeding	
Grade 1	For hemoptysis, interrupt pazopanib and consider whether further treatment with pazopanib is appropriate. For other grade 1 hemorrhage/bleeding event, continue pazopanib at the current dose; monitor as clinically indicated.
Grade 2	Step 1. If pulmonary or GI bleed (other than hemorrhoidal bleeding), discontinue pazopanib and continue follow-up per protocol. Otherwise, interrupt pazopanib until the AE resolved to \leq grade 1. Step 2. Restart pazopanib; consider reducing dose and monitor as clinically indicated.
Grade 3 or 4, or recurrent \geq grade 2 event after dose interruption/reduction.	Discontinue pazopanib and continue with follow-up per protocol.
Venous Thrombosis (DVT, PE)	
Grade 2	Continue pazopanib at the current dose; monitor as clinically indicated

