Grade 3	Step 1. Interrupt pazopanib. Step 2. Initiate and monitor anticoagulation as clinically indicated. Step 3. Resume pazopanib at reduced dose only if all of the following criteria are met: 
 • The subject must have been treated with anticoagulant at the desired level of anticoagulation for at least one week. • No grade 3 or 4 or clinically significant grade 2 hemorrhagic events have occurred while on anticoagulation treatment. Subject should be monitored as clinically indicated during anticoagulation treatment and after resuming study treatment. When treating with warfarin, international normalized ratio (INR) should be monitored within three to five days after any change in pazopanib dosing (e.g., re initiating, escalating/de-escalating, or discontinuing pazopanib), and then at least weekly until the INR is stable. The dose of warfarin (or its derivatives) may need to be adjusted to maintain the desired level of anticoagulation
Grade 4 and/or PE	Discontinue pazopanib and continue follow-up per protocol.
Arterial Thrombosis/Ischemia	
Any grade	Discontinue pazopanib and continue follow-up per protocol.
Thrombocytopenia: Investigate and document underlying cause	
Grade 1 or 2	Continue pazopanib with current dose; monitor as clinically indicated.
Grade 3 or 4	Step 1. Interrupt pazopanib until toxicity resolves to \leq grade 2. Step 2. Restart pazopanib dose-reduced by 200 mg and monitor as clinically indicated. If no recovery to \leq grade 2 or recurrent grade 3 or 4 thrombocytopenia, discontinue pazopanib and follow-up per protocol
Anemia: No specific dose reduction rules are indicated for anemia unless due to hemorrhage or bleeding as noted above.	
Palmar-plantar Erythrodysesthesia Syndrome	
Grade 1 Minimal skin changes or dermatitis without pain (erythema, edema,	Continue pazopanib with current dose.

AE Terms & Descriptions	Dose Modification Algorithms
hyperkeratosis)	
Grade 2 Skin changes with pain; limiting instrumental activities of daily living (peeling, blisters, edema, bleed, hyperkeratosis)	Step 1. Hold pazopanib. Step 2. Treat as clinically appropriate. Step 3. Upon resolution to grade 1 or better, restart pazopanib with a dose reduction to 400 mg. Step 4. If recurrent, consider a further dose reduction to 200 mg or discontinuation.
Grade 3 Severe skin changes with pain and limiting self-care activities of daily living	Discontinue pazopanib
Other Clinically Significant Adverse Events^b	

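### The monthly medication diary prints a fixed 800 mg dose with no field for the assigned dose, so the line is wrong for any patient reduced under Section 6

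*Combined protocol and SAP*

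**What the plan says.** Sections 5.1 and 8.1.6 set the dose at 800 mg once daily, which Section 8.1.6 gives as four 200 mg tablets. Appendix C repeats that dose to the patient as a standing monthly instruction: "Complete one form for each month. Take 800 mg of pazopanib once daily". The diary header asks for date, agent, cycle, patient name and study ID. Its columns are day, date, tablets taken, time of dose and comments. The last item reads: "Please return the forms to your physician or your study coordinator when you go to your next appointment".

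Section 6 lowers the dose for toxicity. As a general rule, "the dose should be reduced stepwise by 200 mg at each step", giving levels of 600, 400 and 200 mg before discontinuation, and "the subject should be monitored for approximately 10 to 14 days at each dose level". The 200 mg level is a working dose with its own rule: there, "a maximum dose delay of 14 days is allowed for management of toxicities". Section 6 also allows the dose to be raised again in 200 mg steps once toxicity has abated.

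The diary is collected and reviewed on Day 1 of each cycle (Section 10) and submitted every cycle (Section 11).

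**The concern.** The diary stays with the patient between visits, and its first instruction names a dose. Once the dose has been reduced, that instruction disagrees with the protocol. The page does not say that 800 mg is only the starting dose, and it has no wording that defers to the site. A patient reduced for toxicity who is handed a fresh page is told again, in writing, to take the full starting dose.

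What is at stake is the safety of patients who have already had a toxicity and clear instructions on a patient-facing form. No estimate or test is at stake.

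**Working it through.** No statistical figure is involved. The check sets the diary beside the dosing rules and does simple tablet arithmetic.

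**Step 1. Does the page hold the assigned dose anywhere?** No. The header has no dose field. The tablet column records what was taken, as item 2 of the diary makes clear, not what should be taken. The table of contents lists one medication diary. The other late appendices are a drug supply form and fax cover sheets for serious adverse events, so no reduced-dose version is listed.

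**Step 2. Are reduced doses part of the plan?** Yes. Seven rows of the adverse event table in Section 6 direct a restart at a lower dose:

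1. Hypertension, scenario B: "restart pazopanib dose-reduced by 200 mg if it was interrupted".
2. Hypertension, scenario C.
3. Proteinuria, UPC or 24-hour protein at 3 or above: "Then restart pazopanib dose-reduced by 200 mg".
4. Venous thrombosis, Grade 3: "Resume pazopanib at reduced dose only if all of the following criteria are met".
5. Thrombocytopenia, Grade 3 or 4.
6. Palmar-plantar erythrodysesthesia, Grade 2 (to 400 mg).
7. Other clinically significant events, Grade 2 or 3.

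An eighth row, Grade 2 bleeding, says only to consider a reduction.

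**Step 3. How far is the print from the assigned dose?** Inputs: tablet strength 200 mg (Section 8.1.4), printed dose 800 mg (Appendix C), dose levels (Section 6). Tablets per day = dose / 200. Ratio = 800 / assigned dose.

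| Assigned dose | Tablets per day | Printed tablets per day | Printed / assigned |
|---|---|---|---|
| 800 mg | 800/200 = 4 | 4 | 800/800 = 1 |
| 600 mg | 600/200 = 3 | 4 | 800/600 = 1.33 |
| 400 mg | 400/200 = 2 | 4 | 800/400 = 2 |
| 200 mg | 200/200 = 1 | 4 | 800/200 = 4 |

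The first row reproduces the four tablets of Section 8.1.6. The print is right at the starting dose and at no other level.

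**Step 4. Can the dose change within a page?** Yes. The page has 28 daily rows, matching a 28-day cycle, while Section 6 monitors each level for about 10 to 14 days. A change, or more than one, can fall inside a page.

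**Step 5. Does anything tell the site to correct the page?** Nothing in the available text does. Sections 5.1, 6, 8.1, 10 and 11 contain no step for amending or reissuing it.

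**The case against.** The strongest reply is that the form records intake and that the site, not the form, sets the dose. The documents call it a diary and list it among the case report forms, and nothing in them lets it override Section 6. In all seven restart rows the lower dose follows a hold or interruption. The patient has been told to stop and must then be told to restart, so a site instruction comes between the printed line and the new dose. Monitoring at each level and the Day 1 review add further chances to catch an error.

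Much of this stands, and it limits the point. It does not remove it, for three reasons. First, item 1 is an instruction, whatever the form is called. Second, not every reduction needs a hold: the general rule in Section 6 allows a stepwise cut without one, and Step 1 of hypertension scenario B offers reduction as an alternative to interruption. Third, diary review looks back at doses already taken, and the safeguards leave the printed line as it was.

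A reader might go further and infer that the form will cause overdosing, perhaps multiplying the daily excess over a whole page. The documents do not support that. It would require the patient to follow the print over the site's instruction for 28 days, and the monitoring to miss it. Nor should the point be read as a fault in the dosing rules, which are clear.

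**Conclusion.** The point holds as a correction to a patient-facing form and should be fixed. The printed instruction agrees with the protocol at dose level 0. It contradicts the protocol at the three reduced levels, where it states 1.33, 2 or 4 times the assigned dose. Those ratios compare the print with the assignment. They do not estimate what patients take.

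The conclusion assumes that the page is issued as printed. Staff may correct it by hand, or the bottle label may carry the assigned dose; the available text shows neither. The documents give no frequency of dose reductions and no evidence of misdosing, so the number of patients affected cannot be stated. A reader might also suspect that the response or progression-free survival results are at risk, but nothing here touches the sample size of 20, the precision statements or the planned analyses.

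**What to change.** In Appendix C, item 1, replace the dose sentence with: *Take ____ mg (____ tablets of 200 mg) once daily, or as most recently directed by your study team.* The site fills in and dates the blanks when each page is issued, and updates them when a dose change is communicated. The closing clause covers a change made within a cycle, so no added visit is required.

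The cost is one line by amendment and a short site entry per page. Dosing rules, visit schedule, sample size and analyses stay as they are.
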